## SYNOPSIS

### Study Title

Secondary stroke prevention by Uniting Community and Chronic care model teams Early to End Disparities: the SUCCEED Trial

### Objectives

[figure not shown]
The primary objectives of this study are as follows:

- (1) To develop a *community-centered component* of a Chronic Care Model-based secondary stroke prevention intervention.
- (2) To test the impact of a sustainable Chronic Care Model-based intervention on control of systolic blood pressure (primary outcome), composite stroke risk, and each individual stroke risk factor (secondary outcomes), among 500 adults (over 90% minority) recruited “early” - during or shortly after hospitalization for an ischemic or hemorrhagic stroke or TIA - at one of the four Los Angeles County safety net medical centers.
- (3) To conduct a cost analysis of SUCCEED from the perspective of the Los Angeles County Department of Health Services, using intervention costs, cost equivalents of associated utilization of county system resources, and cost equivalents of observed and projected vascular events.

### Design and Outcomes

The study design is a multi-center, randomized controlled trial. Patients will be randomized to either a Care Management and Community Health Worker led intervention versus Usual Care to improve management of stroke risk factors. The outcomes of this study will be assessed by a blinded Research Assistant. The total planned enrollment of this trial is 500 subjects. Subjects will be enrolled in the RCT for a period of 1 Year.

### Figure 1. SUCCEED Study Design

We designate systolic blood pressure as the primary outcome for the purpose of sample size calculations. We will assess multiple relevant outcomes including all risk factors and a composite index, cost, quality of life, adverse consequences, moderators, mediators, and a range of metrics of intervention program implementation and participation.

Table 1 below shows the primary and secondary outcomes for SUCCEED.

**Table 1. Primary & Secondary Outcomes**

Primary Outcome
Blood Pressure
Secondary Outcomes
Risk of recurrent stroke, future cardiovascular event
Lipid profile: LDL cholesterol level, Triglyceride level, HDL cholesterol level
Hemoglobin A1c
C-reactive protein (CRP)
Adiposity: Body mass index (BMI), waist circumference, Waist-hip ratio, Waist-to-Height Ratio
Healthy Lifestyle Behaviors & Factors: Physical Activity, Diet, Smoking, Alcohol Use
Death

### Interventions and Duration

We will test the impact of this multi-level, multi-component intervention relative to usual care within the Los Angeles County public safety net healthcare system to improve management of stroke risk factors and increase adoption of healthy lifestyle habits. We will use culturally-adapted educational materials developed by

community-academic partnering teams in our Public Outreach and Dissemination Core. The on study period is 12 months. Additional follow-up off intervention will be every 6 months, up to 18 additional months during the period of center funding.

Data sources include:

- Examinations (Blood pressure, height and weight, waist and hip circumference, NIHSS for stroke severity, Rankin for disability): baseline, 3 months, and 12 months
- Fingerstick laboratory tests (lipid profile, Hgb A1c, CRP) baseline, 3 months, and 12 months
- Full survey: baseline, 3 months, 12 months
- Telephone survey: 8 months
- Telephone surveillance for vascular events and mortality: every 6 months, starting at 12 months, continuing for duration of center funding

Queries of the Los Angeles county administrative database will be conducted when the study is completed for LAC service and medication utilization.

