### **6.2.5 *Final On-Study Evaluations***

The schedule of activities during the final 12 month measurement time point is the same as the baseline and 3 month time points, with the difference being that there is no need to conduct the randomization procedures other than the baseline time points.

After the study is completed, we will call the subjects every 6 months for up to 30 months after randomization to conduct surveillance of vascular events and ascertainment of mortality.

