### **6.2.6 *Off-Study Requirements***

Once the subject has completed the protocol-specified period on study intervention, they will be follow-up with every 6 months for up to 18 months for the occurrence of vascular events and death. Refer to Section 6.1.

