#### 9.2.2 *Secondary outcomes*

Refer to **Table 1** provided below.

**Table 1.** Primary & Secondary Outcomes

Primary Outcome
Blood Pressure (change in blood pressure, as well as proportion of patients with BP under 120/80)
Secondary Outcomes
Risk of recurrent stroke, future cardiovascular event
Lipid profile: LDL cholesterol level, Triglyceride level, HDL cholesterol level
Hemoglobin A1c
C-reactive protein (CRP)
Adiposity: Body mass index (BMI), waist circumference, Waist-hip ratio, Waist-to-Height Ratio
Healthy Lifestyle Behaviors & Factors: Physical Activity, Diet, Smoking, Alcohol Use
Death

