#### **9.5 Data Analyses**

Baseline characteristics between the SUCCEED intervention and usual care groups will be compared. Continuous variable means will be compared using the t-test and ordinal or non Gaussian continuous variables will be compared using the Wilcoxon rank sum test. Unordered categorical variables will be compared using Chi-square test or Fisher's exact test.

Enrollment weights based on a logistic regression model will be calculated using demographic data collected from eligible non-participants. If needed, attrition weights will be determined from logistic regression models using demographic data on participants who drop out of the study. These two weights will be combined to form an overall weight (using the inverse of the product of the probabilities of participation). Both raw and adjusted rates using the overall weight will be compared between SUCCEED and usual care arms.

Intention to treat analyses on all primary and secondary outcomes will be conducted using ordinal logistic or multiple linear regression models, incorporating the overall weight. Intervention status will be an independent variable in all models. We will compare study outcomes between the control and intervention groups both with and without adjusting for potential covariates associated with the outcome measure.

We will test the moderator and mediator effects separately. To assess the moderating effects, we will compare regression models we fit including interaction terms between the independent variables and each possible effect modifier, and the models that do not include the corresponding interaction terms, using the likelihood ratio test (LRT). To assess the mediating effects, we will use Baron and Kenny (1986) methods to run a series of regression analysis and use the Sobel test and Bootstrapping to test mediating effects.

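### Death, and observed vascular events if they are analysed, fall under a logistic or linear regression rule although time at risk can differ between patients and no horizon or censoring rule is stated

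*Combined protocol and SAP*

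**What the plan says.** - **Length of follow-up.** The Synopsis (Interventions and Duration) says: "The on study period is 12 months". It then adds: "Additional follow-up off intervention will be every 6 months, up to 18 additional months during the period of center funding". The data-source list there reads: "Telephone surveillance for vascular events and mortality: every 6 months, starting at 12 months, continuing for duration of center funding". Section 6.2.5 says "we will call the subjects every 6 months for up to 30 months after randomization", and Section 6.2.6 says "every 6 months for up to 18 months for the occurrence of vascular events and death". The schedule in Section 6.1 places the surveillance calls at 18, 24 and 30 months.
- **Outcomes.** Table 1 in Section 9.2.2 lists death as a secondary outcome with no time point. It also lists "Risk of recurrent stroke, future cardiovascular event", without saying whether this is a score or a count of observed events.
- **Analysis.** Section 9.5: "Intention to treat analyses on all primary and secondary outcomes will be conducted using ordinal logistic or multiple linear regression models, incorporating the overall weight". The weight combines an enrolment weight with an attrition weight. The attrition weight is used only if needed and is built from demographic data.
- **Other sources on events.** Section 9.1 collects vascular events by self-report without adjudication and says the later surveillance is meant to inform on the effect of the first 12 months. Sections 6.3.2 and 6.3.3 add a review of administrative databases for stroke, myocardial infarction and death in the study period. Section 6.2.3 attempts a final survey when a patient withdraws.

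No section gives a time-to-event model, a person-time offset, a censoring rule or a fixed horizon for death or vascular events.

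**The concern.** A regression on whether an event occurred gives the same value to a patient event-free for 12 months and one event-free for 30. With follow-up capped by a calendar limit, the resulting proportion refers to no particular length of time and depends on when patients enrolled.

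The more serious issue is loss to follow-up. Section 9.3 expects 20% to 30% attrition. The intervention arm has home visits, classes and calls (Sections 5.1 and 5.4) that usual care lacks, so different loss in the two arms is plausible. A patient lost early must then be counted as event-free, or dropped and represented by weights. The first hides events in the arm with more loss. The second may discard events already reported before the loss. The plan does not say which applies. Leaving the horizon open also lets it be chosen after the data are seen.

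**Working it through.** **1. The plan's own figure.** 12 months on study + up to 18 months = up to 30 months, which matches Sections 6.1, 6.2.5 and 6.2.6. If funding ended as a late enrollee finished the study period, that patient would have 12 months. The possible range in planned time at risk is therefore 30/12 = 2.5-fold. No accrual dates or funding end date are given, so the share of patients with short follow-up cannot be calculated.

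**2. What the range means for absolute risk.** The documents give no event rate, so a constant annual risk is assumed.

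| Assumed annual risk | By 12 months | By 30 months |
|---|---|---|
| 3% | 3.0% | 7.3% |
| 5% | 5.0% | 12.0% |
| 10% | 10.0% | 23.2% |

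With a hazard of 0.08 per year the figures are 1 − e^(−0.08) = 7.7% and 1 − e^(−0.2) = 18.1%. The ratio is about 2.3 to 2.4 throughout.

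**3. Unequal loss, by formula.** Assumptions: hazard h = 0.08 in both arms, a proportion l lost evenly over follow-up T, and lost patients counted as event-free after loss. The observed risk is (1 − l)(1 − e^(−hT)) + l·[1 − (1 − e^(−hT))/(hT)].
- T = 1, l = 0.2: 0.8 × 0.0769 + 0.2 × 0.0390 = 0.0693.
- T = 1, l = 0.3: 0.7 × 0.0769 + 0.3 × 0.0390 = 0.0655.
- Ratio with the heavier loss in control: 0.0693/0.0655 = 1.058, against the intervention. With the loss reversed it is 0.945. At T = 2.5 the ratios are 1.057 and 0.946.

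With 250 per arm this is about 17 v 16 events at 12 months. The standard error of the log risk ratio is about 0.33, so the bias is 0.056/0.33 = 0.17 standard errors. At 30 months it is about 0.27.

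**4. Simulation.** 4,000 runs, 250 per arm, follow-up drawn equally from 12, 18, 24 and 30 months. A logistic comparison of any event (lost patients counted as event-free) was set against an events-per-person-time rate ratio. In the loss scenarios, assumed loss is 30% per year in control and 20% in intervention.

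| Scenario | Annual risk | Logistic | Person-time |
|---|---|---|---|
| Cut-off only, null: type I error | 5% / 10% | 4.4% / 5.3% | 4.3% / 5.1% |
| Cut-off only, hazard ratio 0.6: power | 5% / 10% | 28% / 52% | 28% / 53% |
| Unequal loss, null: estimate | 5% / 10% | 1.14 / 1.14 | 1.01 / 1.01 |
| Unequal loss, null: type I error | 5% / 10% | 5.6% / 7.8% | 4.7% / 4.5% |
| Unequal loss, hazard ratio 0.6: power | 5% / 10% | 16% / 28% | 24% / 44% |

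The simulation standard error of a 5% rejection rate is √(0.05 × 0.95/4000) = 0.34 percentage points, so 7.8% is a clear excess and 5.6% is not. Neither calculation tests the attrition weights, and loss was simulated as unrelated to prognosis.

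**The case against.** - **The funding cut-off is balanced.** Section 4.3.4 allocates 1:1 in blocks of 4, so the calendar limit falls evenly on both arms. A reader might infer that different follow-up by enrolment date itself creates a false treatment difference. The cut-off-only rows above show that it does not. This objection stands in full.
- **The stroke-risk outcome may be a score.** The hypothesis under Primary Objective #2 (Section 1.1) speaks of stroke risk scores at 1 year, and Section 3 mentions a composite index. If that is the meaning, linear regression suits it. This stands, so the point is firm for death and conditional for vascular events.
- **Lost patients are not ignored.** The database review needs no contact, the withdrawal survey may capture some events, and the attrition weights address dropout. These help only in part. The weights are optional and use demographics alone, the databases probably cover only county services, and none of the three fixes a horizon or allows for time at risk.
- **Section 9.1 points to the first 12 months.** It gives a purpose for the later calls, not an analysis window.
- **The size is assumed.** The documents contain no event rate, no loss by arm and no rule that lost patients count as event-free. In the milder scenario the bias is a small fraction of a standard error. This stands.
- **The cost analysis.** A reader might infer that Primary Objective #3 inherits the same error because it uses observed vascular events. That objective names no regression model, so the documents do not show this.

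**Conclusion.** The concern holds in a limited form. Section 9.5 prescribes a method for death, and for observed vascular events if they are analysed, that takes no account of time at risk, and the plan gives neither a horizon nor a censoring rule. The certain consequence is an event proportion without a defined time frame, over which absolute risk could differ about 2.3- to 2.4-fold between the shortest and longest planned follow-up. Bias and loss of power are conditional on loss that differs by arm. They range from slight (null risk ratio about 1.06) to material (null odds ratio about 1.14, power 28% instead of 44% at 10% annual risk), under assumptions on event rate, loss and counting rule that the documents do not supply. The direction depends on which arm loses more patients: heavier loss in control works against the intervention. This is worth correcting before analysis, but it does not touch the primary systolic blood pressure comparison.

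**What to change.** In Section 9.5:
- Exempt death, and observed vascular events if they are analysed, from the logistic/linear rule. Use Kaplan-Meier curves and a Cox model (or a person-time rate model) from randomisation, including site, language and stroke type.
- Censor at the last completed contact or at a stated funding end date.
- Report 12-month cumulative risk by arm as the common-horizon summary.
- State in Table 1 whether the recurrent stroke and cardiovascular risk line means the 1-year score or observed events. Keep linear regression if it is the score.
- If vascular events are analysed without death in the endpoint, say how death is handled as a competing event.

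The cost is wording, plus recording event and last-contact dates from calls and records already planned. There are small downsides. Dates partly rest on recall between six-monthly calls, and Cox still assumes non-informative censoring, so loss related to prognosis is not cured. Restricting the analysis to a 12-month horizon would be simpler, but it discards later events: in the cut-off-only simulation, power at a hazard ratio of 0.6 falls from 28% to 17% at 5% annual risk and from 53% to 35% at 10%.

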**Primary Objective #2:** To test the impact of a sustainable Chronic Care Model-based intervention on control of systolic blood pressure (primary outcome), composite stroke risk, and each individual stroke risk factor (secondary outcomes), among 500 adults (over 90% minority) recruited “early” - during or shortly after hospitalization for an ischemic or hemorrhagic stroke or TIA - at one of the four Los Angeles County safety net medical centers. We will conduct a randomized trial of this intervention that includes the new, community-centered component developed in aim #1, and a “re-engineered” healthcare delivery system with nurse practitioners or physician assistants as care managers, distribution of home blood pressure monitors, group clinics, and a care management software system tailored to secondary stroke prevention and interfaced with the mobile health platform used by the CHWs, relative to usual care. We will include non-English speaking individuals from Hispanic, Chinese, and Korean racial and ethnic groups, and a broad range of stroke severity. We will analyze potential moderators (age, gender, stroke type and severity, education, country of birth/primary language, diabetes comorbidity, care team composition) to understand robustness of intervention impacts across levels of individual and health system characteristics. We will conduct a formative evaluation to continuously improve implementation, and will measure and analyze extent of intervention implementation, as it is delivered for up to 12 months after stroke or TIA through transition of patients into primary care. We will analyze potential mediators (life chaos, competing needs, medication adherence, knowledge of stroke risk factors, participation in self-management programs, social isolation, depression, health literacy, engagement with healthcare provider team, attitudes/health beliefs, self-efficacy, readiness to change, perceived risk, and perceptions of quality of interactions with provider) of the intervention’s impact, using both qualitative and quantitative methods.

*Hypothesis: Patients randomized to the SUCCEED intervention will achieve 8mm greater reduction in systolic blood pressure reduction and lower stroke risk scores at 1 year versus those randomized to usual care.*

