## 4 SELECTION AND ENROLLMENT OF SUBJECTS

The inclusion and exclusion criteria for the SUCCEED RCT are shown below:

**Table 3.** Inclusion and Exclusion Criteria of RCT

Inclusion Criteria

 
Patients of LAC + USC, Rancho Los Amigos, Olive View-UCLA, or Harbor-UCLA with onset of ischemic stroke, hemorrhagic stroke, or TIA within the prior three months.
 

Exclusion Criteria

 
Age < 40 years
 
SBP < 120 mm Hg
 
Speaks language other than English, Spanish, Korean, Mandarin, and Cantonese
 
Cannot provide informed consent due to dementia or aphasia
 

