Please refer to section 4.3.3 for procedures on consent, documenting how subjects learned about the trial, who referred them to the trial, reasons for ineligibility, documentation of ineligibility, and reasons for nonparticipation of eligible subjects. A description of how this information will be collected centrally and used to enhance subject recruitment efforts is also provided.

4.3.3 *Consent (and assent) procedures*

Interaction between the RA and the potential research subject

- *Arranging initial meeting:* When a clinician notifies the RA a face-to-face meeting will be arranged to check whether the patient meets eligibility criteria for enrollment and to describe elements required for informed consent. The RA will read an IRB-approved script that further describes the SUCCEED trial to the patient.

If a potential subject directly contacts the RA using the toll-free number, the RA will read the IRB-approved script that further describes the SUCCEED trial to the patient. If the potential subject is interested, a face-to-face meeting will be scheduled.

- *Setting:* The consent process will take place in a private room. If the meeting takes place in a shared hospital room, the research staff member will close the curtain when meeting with the participant. The RA will describe the study. RA will be bilingual in English or Spanish, but in the case that a subject speaks a language other than English or Spanish, the research team will use volunteers fluent in the appropriate language to translate for the RA.
- *Eligibility:* If interested in continuing, the RA will ask potential subjects questions about age, and onset of stroke to confirm eligibility. They will also take BP measurements. Finally, they will ask questions that require comprehending the basics details of the study. If participants cannot describe what is told to them, they will not be enrolled in SUCCEED. For potential subjects found to be ineligible, the reasons for ineligibility will be recorded.
- *Voluntary consent:* The RA will ensure that eligible subjects are given every opportunity ask questions, and remind the patients that participation in SUCCEED is voluntary. If interested, the potential subject will sign the written consent form. Potential participants will have the opportunity to take the consent document home and discuss participation with others before making a decision.

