#### 6.3.7 *Clinical Assessments*

Because NINDS strongly encourages investigators to make use of the NINDS Common Data Elements in developing the CRFs (see <http://www.commondataelements.ninds.nih.gov/>), the study team will rely on those materials in the development of CRFs for SUCCEED.

**Blood Pressure (BP):** Participants are seated quietly for 5 minutes before Blood Pressure (BP) reading are initiated. Staff are trained to ensure that the proper cutoff size is used and that the participant's arm is resting on a flat surface, with the BP cuff at heart level. Two sequential readings will be taken using the OMRON 90XL with 5 minute intervals between each reading. If the first two readings differ by more than 5mmHg, then an additional two readings are taken and recorded electronically using a laptop based data entry system developed through Core A. Average BP is calculated by the data collection system.

**NIHSS and disability scales:** Each RA will obtain certification to perform the National Institute of Health Stroke Scale (NIHSS) and the modified Rankin scale prior to the start of the study. These are measures of stroke severity and disability. Certification is obtained by completing the following courses and taking a test by scoring an online video of a patient.

<http://nihss-english.trainingcampus.net/uas/modules/trees/windex.aspx> and

<http://rankin-english.trainingcampus.net/uas/modules/trees/windex.aspx?res>.

In addition, the RA will be observed by the site PI for at least the first two study participants. Each RA will be re-observed examining a study participant 2 months later, then 4 months later.

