### 9.3 Sample Size and Accrual

#### **Power Analysis**

Power Analyses was conducted with comparison of main outcomes (systolic blood pressure (SBP)) between the control and intervention arms. Based on availability of patients and our capacity, we plan to enroll 500 subjects from four senior centers. Using Intra-class correlation (ICC) of the four centers at 0.0085 level, attrition after the baseline between 20% to 30% level, mean SBP 141 mm Hg and standard deviation (SD) 20, three repeated measurements: baseline, 3 months, and 12 months (Brown and Prescott 2006), the underlying

statistical power of the study comes from two dimensions of observations: the number of unique subjects and the number of repeated measurements within a subject. Based on sample size and power analyses method proposed by Diggle et al. (1994) and Liu et al. (2005) for repeated measures analysis with a type I error of 0.05, type II error of 0.2 (or equivalent to power of 80%), 2.6 and 2.4 average data points for each subject (corresponding to 20% and 30% attrition respectively), and an auto-correlation at 0.2 level, the effective sample size will be 147 and 147 out of the planned 250 and 250 participants in each of the 2 arms (after adjusting for clustering effect), which will enable us to detect an effect size for SBP as small as 0.215 in standard deviation units or 4.29 mm Hg (for 20% attrition), and 0.253 in standard deviation units or 5.06 mm Hg (for 30% attrition).

The seminal work for moderator and mediator effect was from Baron and Kenny (1986). For potential moderators (e.g., age, gender, stroke type and severity, education, country of birth/primary language), we will test power of moderation using the most common measure of effect size  $f^2$  (Aiken & West, 2001), which equals the unique variance explained by the interaction term divided by sum of the error and interaction variances. Cohen (1988) has suggested that  $f^2$  effect sizes of 0.02, 0.15, and 0.35 are termed small, medium, and large, respectively. A more realistic standard for effect sizes with moderators might be 0.005, 0.01, and 0.025 for small, medium, and large, respectively.

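### The severity moderator can only be the NIHSS at enrolment, taken up to three months after onset, so it measures remaining deficit and partly reflects time since stroke, which no analysis term accounts for

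*Combined protocol and SAP*

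**What the plan says.** - **Severity is a moderator.** Section 1.1, Primary Objective #2: "We will analyze potential moderators (age, gender, stroke type and severity, education, country of birth/primary language, diabetes comorbidity, care team composition". The power analysis in Section 9.3 repeats it: "For potential moderators (e.g., age, gender, stroke type and severity, education, country of birth/primary language".
- **Instrument.** The Synopsis, under Interventions and Duration, lists "NIHSS for stroke severity, Rankin for disability", scheduled at baseline and at 3 and 12 months. Section 6.3.7 has a certified research assistant (RA) perform the NIHSS and Rankin and says "These are measures of stroke severity and disability". No admission score, chart abstraction or retrospective severity score is mentioned.
- **Timing of baseline.** Section 6.2.1 puts screening, baseline and randomization in one face-to-face encounter; Section 4.3.4 has baseline data collected before allocation.
- **Enrolment window.** Table 3 admits patients "with onset of ischemic stroke, hemorrhagic stroke, or TIA within the prior three months". Section 4.3.1 recruits on the wards and in outpatient clinics.
- **Onset.** In Section 4.3.3, "the RA will ask potential subjects questions about age, and onset of stroke to confirm eligibility". No use of this in the analysis is stated.
- **Analysis.** Section 9.5 compares models with and without interaction terms for each candidate effect modifier by likelihood ratio test. Time since onset is not a listed moderator (Section 1.1), a stratification factor (Section 9.1) or a named covariate (Section 9.5).

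**The concern.** An NIHSS taken in the first week and one taken near day 90 do not measure the same thing. If deficits recover at all, a low enrolment score can mean a mild stroke, a more severe stroke seen after recovery, or a TIA whose deficit has resolved. The score therefore carries information about when the patient was enrolled.

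This matters here because Primary Objective #2 stresses early recruitment, which makes time since onset a plausible effect modifier. If the benefit varies with how early a patient is reached, some of that variation would appear in the arm-by-NIHSS term and could be reported as moderation by stroke severity. If the benefit does vary with index severity, the mistimed score weakens the estimated slope somewhat. What is at stake is the interpretation of one exploratory moderator.

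**Working it through.** **Which score can be used.** The Synopsis schedules the NIHSS at baseline, 3 and 12 months. The plan does not say which value enters the moderator model. The later scores are post-randomization and could be affected by the intervention, so baseline is the only suitable one. Because baseline is the enrolment encounter, its time from onset ranges from the inpatient stay to three months.

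**Figure in the plan.** None depends on this point, so there is nothing to reproduce. The size below is illustrative.

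**Inputs from the documents.**
- SBP SD 20 and attrition 20% (Section 9.3): 500 × 0.80 = 400 completers, 200 per arm.
- TIA share of 2009–2011 admissions (Table 2): (173 + 179 + 183) / (1075 + 1144 + 1088) = 535/3307 = 16.2%. This describes admissions, not enrolled patients.

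**Assumed inputs, not in the documents.**
- 30–70% enrolled as inpatients on days 1–7, the rest on days 14–90.
- Index severity gamma (shape 1.5, scale 4).
- Recovered fraction r × (1 − exp(−t/20)), with t in days and r = 0.5 or 0.7.
- TIA scores set to 0.
- A moderation effect of 4 mm Hg per SD of the true moderator.

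**Step 1: how far the score departs from index severity.** Among strokes, repeated simulations gave correlations of about 0.80–0.95 with index severity and −0.23 to −0.40 with time since onset. A separate model (lognormal severity, uniform enrolment over three months, deficit falling 20–60%) gave 0.89–0.997 and about −0.08 to −0.31, on the log scale. With no recovery the correlation with time is zero.

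**Step 2: spurious slope if only time moderates.** The NIHSS slope is roughly the time slope multiplied by the size of the correlation: 4 × 0.23 = 0.92 to 4 × 0.40 = 1.6 mm Hg per SD among strokes. TIA scores of 0 at any time weaken this. The simulated range with TIA included is about 0.7–1.5.

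**Step 3: rejection rate.** For a moderator in SD units, SE = √[20² × (1/200 + 1/200)] = 2.0 mm Hg per SD. Rejection is Φ(−1.96 + δ) + Φ(−1.96 − δ), with δ = slope/SE.
- Slope 0.7: δ = 0.35, giving 0.054 + 0.010 = 6.4%.
- Slope 1.5: δ = 0.75, giving 0.113 + 0.003 = 11.7%.

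Simulation gave about 6–11%, in line with this. Adding arm-by-time returned the slope to about 0 and rejection to 4–6%.

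**Step 4: if severity truly moderates by 4 mm Hg per SD.** The simulated slope is 3.2–3.9 as planned and 3.6–4.0 with arm-by-time added.

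**Step 5: cost of dropping TIA.** 400 × (1 − 0.162) = 335 patients, so SE = 40/√335 = 2.19. Power for a slope of 4 falls from 52% (δ = 2.00) to 45% (δ = 1.83), about 7 points. Simulation gave 6–11 points.

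**The case against.** **The effect is small and conditional.** This stands. Even in the unfavourable scenarios roughly nine trials in ten show no false severity signal. The scenario needs time since onset to moderate by 4 mm Hg per SD, close to the smallest main effect the plan expects to detect (4.29 mm Hg, Section 9.3). Nothing in the documents suggests an effect of that size. Recovery, severity and inpatient share are all assumed, and Primary Objective #2 describes recruitment during or soon after hospitalization, which favours the milder scenarios.

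**Deficit at enrolment is a legitimate moderator.** This also stands. The intervention starts at enrolment and relies on clinics, classes and home visits, so current deficit is relevant. The interaction test is valid for it; the gap is between what is measured and what it is called.

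**Adjustment could remove real severity moderation.** Patients who cannot yet show comprehension cannot enrol, so severe cases may enrol later and time may partly stand for severity. Simulating that link gave a worst-case power change from 0.464 to 0.447. This objection does not hold to any useful extent.

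**Stronger readings.** A reader might infer that the trial will report a severity interaction that does not exist, or that the treatment comparison is biased. The documents support neither. The first goes well beyond rejection rates of 6–11%, and the baseline score precedes randomization. A reader might also conclude that TIA patients should leave this model. They should not: the only stroke-type variable defined (Synopsis, Section 9.1) merges TIA with ischemic stroke, so it could not examine them separately, and the exclusion costs power.

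**Conclusion.** The point holds as one of interpretation, with an inexpensive remedy. The only suitable severity score measures deficit at enrolment, its timing varies by up to three months, and no planned term separates it from time since onset. That much follows from the text, with one inference: that the baseline score is the one used.

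The size does not follow from the text. The slope and rejection figures rest on the assumed recovery, enrolment timing and strong moderation by time; with no recovery, or no moderation by time, there is no spurious signal. The issue is confined to one exploratory moderator. It is a cheap improvement, not a flaw that threatens the trial's conclusions.

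**What to change.** 1. At screening, record the onset date. Section 4.3.3 says onset is asked about but not that a date is kept.
2. In Section 9.5, specify the baseline NIHSS as the severity variable. Add days from onset to the baseline examination, and its interaction with arm, to the stroke-severity moderator model. Judge severity on the arm-by-NIHSS term in that model, comparing it with the model that omits only that term.
3. Report the variable as *NIHSS at enrolment*.
4. Keep TIA patients in the main moderator model; a strokes-only fit is a sensitivity analysis at most.

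The cost is one stored date, a few lines of analysis text and two extra terms in one exploratory model, with essentially no loss of power in the scenarios examined. No visit, procedure or sample size changes.
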